#### 4.2.4 Rationale for Selection of Study Duration

The treatment length in the study is 12 weeks. Based on data from a MAD study (Study D7960C00001), steady state in plasma exposure of AZD0780 was reached after one week of once daily dosing with AZD0780, while steady state in the LDL-C lowering effect was reached within approximately 2 weeks of treatment. With a treatment length of 12 weeks participants are predicted to be at least 10 weeks on stable LDL-C lowering effect, allowing for a robust assessment of the lipid effects of AZD0780. Twelve weeks of dosing is also predicted to allow for a robust assessment of safety, tolerability and the PK of AZD0780 to guide dose selection for further clinical development of AZD0780.

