3.3.1 General Study Level Definitions

Unless otherwise stated, the general principles described below are followed throughout the study:

- Continuous endpoints are summarised by the number of observations, mean, standard deviation (SD), median, first (Q1) and third quartiles (Q3) (as applicable), minimum, and maximum. For data that requires log-transformation (e.g. PK data), we present geometric mean, coefficient of variation (CV), median, minimum and maximum. Categorical endpoints are summarised by frequency counts and percentages for each category.
- Unless otherwise stated, summaries will be presented by treatment group and the following categories will be included:

Table 2 - Presented Treatment groups per Analysis Category

Treatment Group	Study Population	Efficacy Analyses	PK Analyses	Safety Analyses
AZD0780 1 mg	X	X	X	X
AZD0780 3 mg	X	X	X	X
AZD0780 10 mg	X	X	X	X
AZD0780 30 mg	X	X	X	X
AZD0780 Total	X			X
Placebo	X	X		X
Total	X			

- For continuous data, descriptive summary statistics (mean, median, Q1, Q3, SD, 95% confidence intervals (CIs)) are rounded to 1 additional decimal place compared to the original data.
- Minimum and maximum are displayed with the same accuracy as the original data.
- For categorical data, percentages are rounded to 1 decimal place.
- In case of efficacy endpoints, the unscheduled analysis visits are not summarized in tables and figures. They are presented in listings.
- In case of safety endpoints, presentations that are by visit will include data points mapped to scheduled analysis visit windows. For other types of safety outputs, all measured data points will be considered in tables, figures and listings.
- Statistical tests will be performed using 2-sided tests at the 5% significance level, if not explicitly specified otherwise.
- SAS® version 9.4 (as a minimum) is used for all analyses.

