4.2.1.2 Derivations

Direct LDL-C below the LLOQ for which the exact value cannot be determined, will be replaced with the LLOQ divided by the squared root of 2.

Percent change from baseline is derived as:

$$\frac{(y_{V_j} - y_{BL})}{y_{BL}} * 100$$

where

- y_{V_j} represents the efficacy measurement at Visit j , and
 - j refers to the visit number, specifically 3,4,5,6,7 (i.e., the visits included in the analysis),
 - In case of treatment discontinuation ICE, j includes all visits up to and including the date of treatment discontinuation.

- For every other ICE handled with the hypothetical strategy, j refers to the last visit before the first ICE occurrence handled with the hypothetical strategy, as detailed in Section 3.3.1.4.
- y_{BL} is the efficacy measurement at Baseline.

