4.2.1.4 Primary Analysis of Primary Endpoint

The summary measure for the primary endpoint will be the difference in least squares mean of percent change from baseline of direct LDL-C at Week 12. The primary endpoint will be analysed using a MMRM on the FAS. Percent change from baseline in direct LDL-C at each post-baseline visit will be used as the dependent variable. The model will include the fixed effects of baseline direct LDL-C, treatment group, visit, and treatment-by-visit interaction, and the random effect (random intercept) of participant. The Restricted Maximum Likelihood estimation approach will be used with a compound symmetry covariance structure for repeated measures.

In case of non-convergence, an ANCOVA model will be run. The model will include the fixed effects of baseline direct LDL-C and treatment group as covariates. In this model, the dependent variable will be the percent change in direct LDL-C from baseline to Week 12.

The results will be summarized by the difference in least squares means, 95% confidence interval, and p-value.

The hierarchical testing strategy will be employed to strongly control the familywise error rate at the 0.05 level (2-sided), as described in Section 3.3.3.

The primary endpoint will also be characterized by descriptive statistics (as defined in Section 3.3.1) at each scheduled visit and visualized with line plot.

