4.2.1.5 Sensitivity Analyses of the Primary Endpoint

No sensitivity analysis is planned for the primary estimand.

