4.2.1.6 Supplementary Analyses of the Primary Endpoint

The supplementary analysis of the primary endpoint using the primary estimand will be conducted by replacing the direct LDL-C with the LDL-C derived from the Friedewald equation with reflex ultracentrifugation using the analysis model specified in Section 4.2.1.4.

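### The primary Week 12 test takes its standard error from a variance pooled over five visits, and no planned inferential analysis relaxes that assumption

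*SAP*

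**What the plan says.** SAP 4.2.1.4 models percent change in direct LDL-C at each post-baseline visit. The fixed effects are baseline, treatment, visit and treatment-by-visit, with a participant random intercept, and "The Restricted Maximum Likelihood estimation approach will be used with a compound symmetry covariance structure for repeated measures". Protocol 9.4.2.1 specifies the same model, and protocol 9.4.2.2 carries it to the other lipid endpoints.

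In SAP 4.2.1.2 the visit index "refers to the visit number, specifically 3,4,5,6,7 (i.e., the visits included in the analysis"; the Schedule of Activities places these visits at Weeks 1, 2, 4, 8 and 12. Only the Week 12 difference is tested, dose by dose in fixed sequence at two-sided 0.05 (SAP 3.3.3).

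On alternatives:
- SAP 4.2.1.5: "No sensitivity analysis is planned for the primary estimand".
- The Friedewald supplementary analysis is run "using the analysis model specified in Section 4.2.1.4". The subgroup analyses (4.2.1.7) and the treatment-policy analysis with its two sensitivity analyses (4.2.2.4 and 4.2.2.5) use the same model.
- "In case of non-convergence, an ANCOVA model will be run" (SAP 4.2.1.4). SAP Appendix A repeats this for the imputed analyses and also lets ANCOVA be considered there if between-imputation variability is zero.
- "The primary endpoint will also be characterized by descriptive statistics" at each scheduled visit, and SAP 3.3.1 defines what these contain: "Continuous endpoints are summarised by the number of observations, mean, standard deviation (SD), median" and further statistics.

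**The concern.** Compound symmetry gives every visit the same variance. The Week 12 contrast is the only one tested, yet its standard error borrows variance from four other visits. If the visits differ in variance, the Week 12 p-value and interval are miscalibrated. Neither more participants nor convergence of the model corrects this.

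At stake is the statement in SAP 3.3.3 and 4.2.1.4 that the familywise error is strongly controlled at 0.05. In a fixed sequence, that control is no better than the actual level of the first true null reached. Under the global null it equals the level of the first test. The interval widths that inform dose choice are affected by the same factor. A table of SDs by visit would make a clear difference visible, but it changes no p-value or interval.

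**Working it through.** **The plan's own figures.** Protocol 9.2 goes from 375 randomized to about 320 evaluable at 15% discontinuation: 375 × 0.85 = 318.75, and 320 / 5 = 64 per arm. This reproduces. The effect and SD are blacked out, so the statement of more than 90% power cannot be recomputed. It can only be inverted: (1.960 + 1.2816) × sqrt(2/64) = 3.2415 × 0.1768 = 0.573, so 90% power needs an effect of at least 0.573 SD. That calculation is a two-sample t-test on the Week 12 change, so it does not involve variance pooled over visits.

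**Formula.** With complete data, equal arm sizes and equal arm variances, the Week 12 contrast has true SE sqrt(2·V12/n). Compound symmetry replaces V12 by the mean of the five visit variances. Hence

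r = model SE / true SE = sqrt(mean visit variance / V12),

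level = 2·P(Z > 1.96·r), and power = P(Z > 1.96·r − 3.2415) for a design with 90% power under the correct SE.

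**Inputs.** Five visits and alpha 0.05 come from the SAP. No visit-specific SD is given, so every profile below is an assumption.
- Week 1 SD m times the other four: r² = (4 + m²)/5.
- Week 12 SD k times the other four: r² = (4 + k²)/(5k²).

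| Assumed profile | r² | 1.96·r | Level | Power (90% nominal) |
|---|---|---|---|---|
| All visits equal | 1.000 | 1.960 | 5.0% | 90% |
| Week 1 SD 0.8× | 0.928 | 1.888 | 5.9% | 91% |
| Week 1 SD 0.9× | 0.962 | 1.922 | 5.5% | 91% |
| Week 1 SD 1.1× | 1.042 | 2.001 | 4.5% | 89% |
| Week 1 SD 1.2× | 1.088 | 2.044 | 4.1% | 88% |
| Week 12 SD 0.9× | 1.188 | 2.136 | 3.3% | 87% |
| Week 12 SD 1.05× | 0.926 | 1.886 | 5.9% | 91% |
| Week 12 SD 1.1× | 0.861 | 1.819 | 6.9% | 92% |

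Power above 90% in the table is bought with the inflated level. Coverage of the 95% interval is 100% minus the level, for example 93.1% in the last row.

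**Threshold.** The level reaches 6% when V12 / mean variance = (1.960/1.881)² = 1.086, which is a Week 12 SD about 1.05 times the others.

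**Arm pooling.** The variance is also pooled over arms. If the four active SDs are c times placebo, r² gains the factor 2(1 + 4c²)/(5(1 + c²)). With c = 1.25 the factor is 1.132. Combined with Week 12 SD 1.05×, r² = 1.132 × 0.926 = 1.048 and the level is 4.5%. A Week 12 variance above the mean therefore does not inflate the level by itself; equal arm variances are needed too.

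**Check of the formula under dropout.** A REML compound-symmetry fit was simulated with 5 × 75 participants, five visits, exchangeable or AR(1) correlation 0.6, 0% or 15% monotone dropout, and 3,000 null runs per scenario. At V12 / mean variance 0.66 the formula gives 1.6% and simulation 1.5% to 1.7%. At 1.485 they give 10.8% and 10.2% to 11.5%. With equal variances, AR(1) and 15% dropout the simulated level was 5.2%. Week 12 ANCOVA held 4.6% to 5.6% in the unequal-variance scenarios. These wide ratios were chosen to test the formula and are not estimates for this trial.

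**The case against.** The case for leaving the model alone is substantial.

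- **No evidence of unequal variances.** A reader might infer a Week 1 difference from protocol 4.2.4, which says "steady state in the LDL-C lowering effect was reached within approximately 2 weeks of treatment". The sentence does not support that. It gives an upper bound on the time to a stable effect, so it does not place Day 8 before steady state, and it concerns the effect, not its variance. Nothing suggests a distinct Week 12 SD either. The primary estimand also drops measurements after treatment discontinuation, background-therapy change and prohibited lipid-affecting medication (SAP 4.2.1.1 and 4.2.1.2), which removes some obvious sources of late variance growth. This stands, and it is why the figures are illustrations only.
- **Small and two-sided.** For modest Week 1 differences the level moves by about a point or less, in either direction. This stands.
- **ANCOVA may run anyway.** A random intercept plus a compound-symmetry residual parameterises the same covariance twice. If that literal model fails to converge, the SAP moves to a Week 12 ANCOVA without the constraint. The documents do not settle which model would run. But convergence failure is a different trigger from unequal variances, so this is no safeguard.
- **Consistent prespecification in a Phase IIb study sized for safety.** True, and it limits the consequence. It does not supply a check on the assumption.

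**Conclusion.** The point holds as a conditional risk, between minor and should-fix. The Week 12 standard error depends on equal residual variances across visits and arms. The documents give no reason to rely on that equality, and no planned inferential analysis drops it unless the model fails to converge or, for the imputed analyses, the zero-variability option is taken up.

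The size is unknown. Under the assumed profiles the level runs from 3.3% to 6.9%, with power down to 87% at the conservative end. These figures rest on complete data and equal arm variances.

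A reader might go further and conclude that the primary test is anti-conservative or that the familywise claim is false. The documents do not support that: no SD by visit is given, the direction could be either way, and differences between arms can offset differences between visits. Nor can one conclude that the study is underpowered, since the planning effect and SD are blacked out.

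**What to change.** **Preferred.** In SAP 4.2.1.4 and protocol 9.4.2.1 to 9.4.2.2, specify an unstructured within-participant covariance with Kenward-Roger degrees of freedom and no additional random intercept. Add a short ordered fallback for non-convergence, for example heterogeneous Toeplitz, then compound symmetry with a participant-clustered sandwich SE, then the Week 12 ANCOVA.

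**Minimum.** If compound symmetry stays primary, replace SAP 4.2.1.5 with one sensitivity analysis: unstructured covariance, a participant-clustered sandwich SE, or the Week 12 ANCOVA already specified. State whether the random intercept or the compound-symmetry residual is fitted.

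**Cost.** Wording, a few lines of code and no new data. Unstructured has 5 × 6 / 2 = 15 covariance parameters instead of 2, which about 375 participants with five visits can support. The minimum version costs one extra analysis.

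**Limits.** An unstructured covariance common to all arms does not deal with unequal variances between arms. In simulation with 15% dropout completely at random and active SDs 0.8 times placebo at every visit, compound symmetry gave 6.7% to 7.2%, unstructured 6.2% to 7.2%, ANCOVA 6.5% to 6.9% and the sandwich SE 4.5% to 5.5%. The unstructured fit there used a simple degrees-of-freedom scaling, so Kenward-Roger itself was not simulated. The sandwich corrects only the SE; it does not change the point estimate under missing-at-random dropout.

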#### 9.4.2.1 Primary Endpoint(s)

The primary endpoint is percent change from baseline of LDL-C at Week 12. This will be assessed for each dose of AZD0780 versus placebo. The hypothetical estimand will be used for this endpoint. With the hypothetical estimand, LDL-C measurements taken after the occurrence of intercurrent events would not be used for effect estimation. More details on estimand are provided in Section 3.

The summary measure for the primary endpoint will be least squares mean of percent change from baseline of LDL-C at Week 12. The primary endpoint will be analyzed using a MMRM based on the FAS population. The model will include the fixed effects of baseline, treatment, visit, and treatment-by-visit interaction, and the random effect (random intercept) of participant. The Restricted Maximum Likelihood estimation approach will be used with a compound symmetry covariance structure for repeated measures. The treatment effects will be summarized by the difference in least squares means, 95% confidence interval, and p-value.

The hierarchical testing strategy will be employed to strongly control the familywise error rate at the 0.05 level (2-sided), as described in [Section 9.1](#).

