4.2.1 Primary Endpoint

4.2.1.1 Definition

The primary efficacy endpoint is percent change from baseline to Week 12 in direct LDL-C. The clinical question of interest is:

What is the difference in means of percent change in LDL-C from baseline to Week 12 in participants with dyslipidemia treated with AZD0780 vs placebo in the hypothetical condition that all participants could adhere to study intervention and non-prohibited

background lipid lowering statin and non-statin therapy, prohibited medications affecting lipid parameters were not available, regardless of whether additional treatment is used, where participants cannot die.

The primary estimand attributes are defined as:

- Treatment: AZD0780 or placebo.
- Population: Male and female participants of non-childbearing potential, 18 to 75 years of age with dyslipidemia, defined by the inclusion and exclusion criteria. Implemented using FAS.
- Endpoint: Percent change in direct LDL-C from baseline at Week 12.
- Population-level summary measure: Difference in means of percent change in direct LDL-C from baseline to Week 12 between AZD0780 and placebo.
- Handling of intercurrent event: The hypothetical strategy will be used for premature and permanent discontinuation of study treatment; change in background lipid lowering statin therapy; initiation, change or discontinuation in non-prohibited background lipid lowering non-statin therapy and intake of prohibited medications affecting lipid parameters. Efficacy assessments obtained after these will not be included in the analysis. Initiation or changes in other concomitant or prohibited medication will be handled with treatment policy strategy. Deaths will be handled with a hypothetical strategy.

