4.2.1.3 Handling of Dropouts and Missing Data

Missing baseline measurements

Missing baseline values will not be imputed.

Non-monotone missing data

Non-monotone missing data means that observations exist after the time point with the missing data.

Non-monotone missing data will not be explicitly imputed.

Monotone missing data

Monotone missing data are defined on a participant level as missing data that constitutes the end of participant follow-up.

Monotone missing data will be assumed to be Missing at Random (MAR) and will not be explicitly imputed.

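### The primary MMRM states within-participant correlation twice, and its only fallback on non-convergence is an ANCOVA that drops everyone without a usable Week 12 value

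*SAP*

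**What the plan says.** **Model.** SAP 4.2.1.4 fits an MMRM to percent change in direct LDL-C at the five post-baseline visits (Visits 3 to 7, SAP 4.2.1.2). Fixed effects are baseline, treatment, visit and treatment by visit. It then adds "and the random effect (random intercept) of participant. The Restricted Maximum Likelihood estimation approach will be used with a compound symmetry covariance structure". Protocol 9.4.2.1 has the same pair: "and the random effect (random intercept) of participant", together with compound symmetry.

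**Fallback.** SAP 4.2.1.4: "In case of non-convergence, an ANCOVA model will be run". Its covariates are limited: "The model will include the fixed effects of baseline direct LDL-C and treatment group as covariates". Its outcome is a single value per participant: "In this model, the dependent variable will be the percent change in direct LDL-C from baseline to Week 12". Protocol 9.4.2.1 has no such fallback, and SAP Section 2 does not list it among the changes to the protocol's analyses.

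**Missing data.** SAP 4.2.1.3: "Monotone missing data will be assumed to be Missing at Random (MAR) and will not be explicitly imputed", and "Non-monotone missing data will not be explicitly imputed". For the intercurrent events handled hypothetically, SAP 4.2.1.1 adds: "Efficacy assessments obtained after these will not be included in the analysis".

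**Elsewhere.** SAP 4.2.1.5 plans no sensitivity analysis for the primary estimand. For the treatment-policy analyses, SAP Table 12 (Step 3) also allows ANCOVA on convergence problems, but on data that have already been imputed.

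**The concern.** There are two linked weaknesses.

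First, a participant random intercept and a compound-symmetry residual describe the same covariance. Including both leaves the variance parameters without a unique solution. This is the kind of model that can produce singularity warnings or stop.

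Second, the plan does not say what counts as non-convergence, and there is no step between the MMRM and the ANCOVA. The ANCOVA has no imputation and no post-baseline covariate. It can therefore use only participants with a Week 12 value obtained before any hypothetically handled intercurrent event.

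At stake is the missing-data assumption of the alpha-controlled test. A numerical flag could swap missing at random given the earlier visits for a stronger assumption that the SAP does not state, and no planned sensitivity analysis would show the difference. The same model is reused for the Friedewald supplementary analysis, each subgroup and the ten other lipid and inflammatory endpoints. The smaller subgroup fits inherit the same weakness.

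**Working it through.** **Inputs from the documents.** 375 randomized 1:1:1:1:1, about 320 completers (64 per arm), 15% discontinuation, two-sided alpha 0.05, power above 90% (Protocol 9.2); five post-baseline visits (SAP 4.2.1.2). The planning effect and SD are redacted, so every SD, correlation, effect and dropout mechanism below is an assumption.

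**1. The plan's own figure.** 320 / 0.85 = 376.5, against 375 stated. Forward: 375 x 0.85 = 318.75, or 63.75 per arm, against 64. The sample size reproduces.

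**2. Redundancy.** Let s_b be the random-intercept variance, c the compound-symmetry covariance and s_e the residual variance. Over five visits

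V = s_b J + c J + s_e I = (s_b + c) J + s_e I.

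The derivatives of V with respect to s_b and c are both J. Two rows of the information matrix are therefore identical: its rank is 2 of 3, with one eigenvalue equal to zero. On simulated data with s_b + c = 540 and s_e = 360, the -2 log-likelihood is 13654.478595 at each of the splits 540/0, 400/140, 270/270, 100/440, 0/540 and -100/640. V is the same at every split, so the generalized least squares treatment contrasts are the same too. With the correlation stated once, the rank is 2 of 2.

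**3. Who leaves under the fallback.** 375 x 0.15 = 56.25, so about 56 participants have no usable Week 12 value. In the simulation below each had about 2.4 earlier visits, so roughly 56 x 2.4 = 134 LDL-C records are discarded. Intercurrent events other than treatment discontinuation would add to this.

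**4. Assumption needed.** The MMRM needs missingness to be unrelated to the unseen value given baseline, arm and the observed earlier visits. The ANCOVA needs it to be unrelated given baseline and arm only.

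**5. Size, all arms.** Simulation of 5 arms of 75, five visits, about 15% monotone dropout, 3000 replicates. Under response-dependent dropout, the log-odds of leaving rise by 1 per SD of the previous value. Entries are bias in percentage points (model SE):

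| SD | Correlation | Dropout | ANCOVA | MMRM, compound symmetry |
|---|---|---|---|---|
| 20 | 0.5 | completely at random | 0.01 (3.55) | 0.00 (3.45) |
| 20 | 0.7 | completely at random | 0.03 (3.55) | 0.01 (3.39) |
| 20 | 0.5 | active arms only | -1.57 (3.47) | 0.00 (3.43) |
| 20 | 0.7 | active arms only | -2.12 (3.43) | 0.02 (3.37) |
| 30 | 0.5 | active arms only | -2.36 (5.21) | 0.00 (5.15) |
| 30 | 0.7 | active arms only | -3.18 (5.14) | 0.03 (5.06) |

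With the same response-dependent mechanism in every arm, ANCOVA bias lies between -0.02 and 0.00. The biased cases amount to 1.57 / 3.47 = 0.45 to 3.18 / 5.14 = 0.62 of one SE. The negative sign overstates LDL-C lowering, and follows from assuming that participants with higher values leave. Under completely random dropout the ANCOVA SE is 3% to 5% larger (3.55 / 3.45 = 1.03; 3.55 / 3.39 = 1.05).

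**6. Size, smaller SDs.** Two arms of 75, between- and within-participant SDs 14 and 12, assumed effect -45, about 15% dropout after Week 4 that depends on the Week 4 value in the active arm only. Repeated runs give completer bias of -0.5 to -0.9 at log-odds 0.5 per SD and -1.4 to -1.7 at 1.0. Compound symmetry on all visits gives between -0.05 and 0.14.

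**7. A simpler structure does not rescue it.** In the same setting without a baseline covariate, an all-visit model with independent errors reproduces the completer bias exactly: -0.68 and -1.42, against 0.14 and -0.01 for compound symmetry. Without within-participant correlation, the earlier visits say nothing about Week 12.

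**8. Power.** With 64 per arm, 90% power needs effect / SD = (1.960 + 1.282) x sqrt(2/64) = 0.573. Protocol 9.2 bases this on completers in a t-test, which is close to what the fallback does.

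**The case against.** A reader might infer that the double specification will make the primary fit fail. The documents do not support that. Non-identified variance parameters are not the same as non-convergence: software may set one component to zero and return the intended fixed effects. The text can also be read as one model described in two ways, since a random intercept induces compound symmetry. Coded once, the model has two covariance parameters for about 375 participants, and failure is remote. No failing fit has been shown. All of this stands, so the double specification is a risk and not a demonstrated cause.

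A reader might also infer that the fallback estimate would be biased. That needs dropout to depend on LDL-C response differently in active and placebo arms. Laboratory results that could unblind are withheld from sites (Protocol 8), rescue medicine is not applicable (6.9.1), and no stopping criterion in 7.1 rests on LDL-C. An indirect route through adherence or tolerability remains possible, but nothing in the documents gives its strength. Against the assumed effect of -45, a bias of 0.9 to 1.7 points is 2% to 4% and would be unlikely to change a test.

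Nor does the fallback cost planned power or change the nominal analysis population: the sample size already counts completers only, and the full analysis set stays as defined. The treatment-policy analyses are not exposed to the complete-case loss, because imputation precedes their ANCOVA.

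What survives is that the primary model is over-specified as written, its trigger is undefined, and its fallback contradicts the SAP's own missing-data assumption.

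**Conclusion.** The point holds as a minor one. The redundancy is algebra and does not depend on any redacted figure. The restriction of the fallback to usable Week 12 values follows from SAP 4.2.1.1, 4.2.1.3 and 4.2.1.4 read together. At the planning rate it removes about 15% of participants from the primary test and replaces missing at random given earlier visits with a stronger assumption.

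The bias, if the fallback is used, ranges from about 0 to roughly -3 percentage points. It is about 0 when dropout is completely at random or acts alike in every arm. It is roughly -0.5 to -3 under assumed SDs and an assumed response-dependent mechanism confined to the active arm or arms. The probability of reaching the fallback is unknown and probably low. If the MMRM converges, the treatment contrasts are the intended ones.

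**What to change.** 1. Delete the random intercept in SAP 4.2.1.4 and Protocol 9.4.2.1 (with the matching synopsis and secondary-endpoint text). Keep one identifiable within-participant covariance: compound symmetry in the repeated structure. The intended marginal covariance and contrasts are unchanged.
2. Define non-convergence, and state that a Hessian or G-matrix warning alone does not trigger the fallback.
3. If the model truly fails, first try other starting values or another optimiser, or another identifiable structure that keeps within-participant correlation, using all visits. Exclude independence from that list.
4. As a last resort, run the ANCOVA after missing-at-random multiple imputation by arm, using baseline and the visits before any hypothetically handled intercurrent event. This needs its own imputation step. Table 12 is not a ready template, because its Step 2 imputes monotone values after an intercurrent event under a missing-not-at-random model.

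The cost is SAP wording, one protocol clarification and a little programming, with no loss of power.
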